9.2. Schedule of Events

9.2.1. Visit Schedule

10768467DOC

Figure 5. Visit Schedule Flowchart

9.2.2. Visit 1: Consent and Screening

Overview General

Investigational center staff will:

- Obtain ICF from the subjects
- Assess subject eligibility to participate in the study
- Obtain demographic and baseline characteristics including:
 - Age
 - Gender
 - o Race
 - Ethnicity
 - Height and Weight

Note: Body Mass Index (BMI) will be calculated automatically in the study database, based on height and weight measurements entered.

- Concomitant medications (Screening Only)
- Type of diabetes
- Date of diabetes diagnosis
- Complete required screening tests, if all eligibility criteria are met:
 - o Perform urine test for pregnancy, female subjects of child bearing age or capability
 - Obtain blood sample for Hct
 - Send to local laboratory for required screening tests. (There is no point of care (POC) testing for Hct).
 - Subjects may not participate in the study training without Hct; Hct value must be reviewed for exclusion criteria prior to Visit 2
 - Note: For out of range Hct lab result, a single re-test is permitted
- Obtain blood sample and send to local laboratory for A1C (not an eligibility criteria)
- Enter eCRFs into the study database as appropriate
- Schedule next visit date and time

The study is open to all individuals who meet the eligibility criteria of the study. The investigational center will be responsible for determining adequate source documents to verify subject eligibility. Subjects who do not meet the eligibility requirements for participation in the study will be entered into the database as screen failures. Applicable eCRF(s) will be completed for all subjects who signed an ICF, whether they are eligible or ineligible to participate. If a subject fails screening criteria (e.g. Hct or pregnancy test) they will be notified regarding their

CIP320 Clinical Investigation Plan 10768467DOC Version C Page 40 of 97 Medtronic

ineligibility immediately, either in person or via telephone). Eligible subjects will return to the investigational center to be randomly assigned and begin study training at Visit 2.

Visit 2 may be completed on the same day as Visit 1, provided that Hct and pregnancy test results are available and all other eligibility criteria are met.

9.2.3. Visit 2: Random Assignment

Visit 2 can be done the same day as Visit 1 if all eligibility criteria on Visit 1 is met, including review of Hct. Visit 1 and Visit 2 should be no more than 2 weeks apart.

Overview general study procedures

Investigational center staff will:

- Confirm subject eligibility prior to moving forward with any study procedures
- Randomly assign eligible subjects
 - o Subjects will not be blinded to the investigational devices used.
 - Subjects will be randomly assigned to one of the following sensor wear Day 1, 3-5, or 7, which determines when they will be participating in the in-clinic YSI™* FST.
- Enter eCRFs into the study database as appropriate
- Schedule the next visit date and time
- The YSI™* FST visits may be scheduled at this visit by the investigational center staff. The visits will be scheduled so that YSI™* FST timing and fingerstick glucose reading requirements are conducted as displayed in Table 2.

10768467DOC Version C Page 41 of 97 Medtronic

9.2.3.1. Procedures Including YSI™* FST Timing, SMBG, and Calibration Requirements

Table 2. YSI™* FST Timing, SMBG, and Calibration Requirements

Visit	Sensor Wear	Group	Timing of YSI™* FST from Sensor Insertion T=0	Calibration Requirements In-Clinic	Calibration Requirements at Home	SMBG
4	Day 1		The 7 hours FST may be performed anytime between T=2 to 26 hours	 Time = 0 hour Guardian™ Sensor (3) insertions will be performed at the investigational center The 0 hour represents the time after sensors have been connected to the last of the Guardian™ Connect transmitter(s). 1st Calibration- T = 30 minutes to 2 hours after the Guardian™ Sensor (3)s have been connected to the Guardian™ Connect transmitter(s). The Subject should calibrate when a "Calibrate Now" Alert is received from the Guardian™ Connect app T = 2 hours 	Calibration at home will be required to be 3-4 times spread throughout the day using the Guardian™ Connect app or if device prompts for calibration (i.e. Smart Calibration feature).	 Approximately T = 2 hours after the sensors were connected to the transmitters Approximately T=8 hours after the sensors were connected to the transmitters Fingerstick testing will be recommended to be a minimum of 4 times spread throughout the day. (Record in Patient Log Sheet if CONTOUR™* study meter BG software and cable is not accessible at time of the study start) At the end of FST take one finger stick glucose reading

10768467DOC Version C Page 42 of 97

Visit	Sensor Wear	Group	Timing of YSI™* FST from Sensor Insertion T=0	Calibration Requirements In-Clinic	Calibration Requirements at Home	SMBG
				YSI™* FST period begins.		
				 2nd Calibration- T = Within 6 hours after first calibration. The Subject should calibrate when a "Calibrate Now" Alert is received from the Guardian™ Connect app. 		
				 Calibration should be performed during YSI™* FST if the Guardian™ Connect app prompts for calibration (i.e., Smart calibration feature) 		
4	Day 3-5	Day 3- 5	The 7 hours FST may be performed anytime between Time= 50 to 122 hours (±6)	 Calibration approximately at start of YSI™* FST. Calibration should be performed during YSI™* FST if the Guardian™ Connect app prompts for calibration (i.e., Smart calibration feature) 	Calibration at home will be required to be 3-4 times spread throughout the day by the Guardian™ Connect app or if device prompts for calibration (i.e. Smart Calibration feature).	 Fingerstick testing will be recommended to be a minimum of 4 times spread throughout the day. (Record in Patient Log Sheet if CONTOUR™* study meter BG software and cable is not accessible at time of the study start) At the end of FST take one finger stick glucose reading

Medtronic

10768467DOC Version C Page 43 of 97

Visit	Sensor Wear	Group	Timing of YSI™* FST from Sensor Insertion T=0	Calibration Requirements In-Clinic	Calibration Requirements at Home	SMBG
4	Day 7	Day 7	The 7 hours FST may be performed anytime between Time = 146 hours to 170 hours	 Calibration approximately at start of YSI™* FST. Calibration should be performed during YSI™* FST if the Guardian™ Connect app prompts for calibration (i.e., Smart calibration feature) 	Calibration at home will be required to be 3-4 times spread throughout the day by the Guardian™ Connect app or if device prompts for calibration (i.e. Smart Calibration feature). Calibrations after YSI™* FST Day Calibration at home will be required to be 3-4 times spread throughout the day by the Guardian™ Connect app or if device prompts for calibration (i.e. Smart Calibration feature).	 Fingerstick testing will be recommended to be a minimum of 4 times spread throughout the day (Record in Patient Log Sheet if CONTOUR™* study meter BG software and cable is not accessible at time of the study start) At the end of FST take one finger stick glucose reading

Medtronic

10768467DOC Version C

9.2.4. Visit 3: Study Training & Sensor Insertion

The main purpose of Visit 3 is to provide subjects with study procedure training and sensor insertions. The subjects will receive training on the study requirements before completing the FST visit.

9.2.4.1. Overview General Study Procedures

Investigational center staff will:

- Provide subject with the opportunity to bring up study-related questions and concerns
- Ask subject about the occurrence of AEs
 - Record AEs on the appropriate eCRF, if subject reports health status changes that result in a new medical condition or deterioration of an existing medical condition, such as sickness or glycemic problems.
- Ask subject about device deficiencies
- Prepare all study devices following the instructions in the instructions for use (IFU) including the following:
 - Synchronize time on Guardian™ Connect app and CONTOUR™* study meter using investigational center's designated study clock
 - Synchronize study laptop computer at the investigational center using investigational center's designated study clock
 - Fully charge the transmitter(s) prior to distribution to study subject
- Perform applicable quality control (QC) testing (CONTOUR™* study meter). Shake control solution bottle well prior to use. QC should be performed:
 - o prior to dispensing a CONTOUR™* study meter
 - o any time additional strips are given to the subject
- Instruct trained subject to self-insert Guardian[™] Sensor (3)s into the abdomen area and perform connection of Guardian[™] Sensor (3)s to the Guardian[™] Connect transmitters. It is up to investigator's discretion on which Guardian[™] Sensor (3) will be connected to the Guardian[™] Connect transmitter and paired to the Guardian[™] Connect app.
- Document time of insertion
- Calculate T=170 hours where the sensor may be removed at that time or after that time.
- Instruct trained subject to self-apply the sensor tape according to the user guide
- Instruct subject that sensors may be inserted on same side or opposite sides.
- Inform subjects that observation by sponsor may occur at any time during the study
- Review requirements and schedule study visit with subjects

10768467DOC Version C

- Review the visit date and time for YSI™* FST
- Remind subject to bring any medication, syringes, insulin, that might be needed to treat his/her diabetes during the YSI™* FST visit.
- Enter eCRFs into the study database as appropriate

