5.2. Endpoints

5.2.1. Primary Endpoints

Guardian™ Sensor (3) connected to a Guardian™ Connect transmitter and paired to the Guardian Connect app will be the primary sensor.

1a) Sensor values from primary sensor will be compared to YSI™* plasma glucose values during YSI™* FSTs. A within 20% agreement rate (±20 mg/dL (1.1 mmol/L) when Reference BG less than or equal to (≤) 80 mg/dL (4.4 mmol/L) between Guardian™ Sensor (3) values and YSI™* plasma glucose values during YSI™* FST days defined as p will be evaluated against the null Hypothesis:

H0: p ≤ 60%

H1: p > 60%

1b) Sensor values from primary sensor will be compared to YSI™* plasma glucose values during YSI™* FSTs. A mean rate in Zone A+B of Consensus Error Grid between Guardian Sensor (3) values and YSI™* plasma glucose values during YSI™* FST days defined as p will be evaluated against the null Hypothesis:

H0: p ≤ 90%

H1: p > 90%

10768467DOC Version C

Page 23 of 97 Medtronic

1c) Sensor values from primary sensor will be compared to YSI™* plasma glucose values during YSI™* FSTs. A mean rate in Zone A+B of Clarke Error Grid between Guardian Sensor (3) values and YSI™* plasma glucose values during YSI™* FST days defined as p will be evaluated against the null Hypothesis:

H0: p ≤ 90%

H1: p > 90%

1d) Sensor values from primary sensor will be compared to YSI^{TM*} plasma glucose values during YSI^{TM*} FSTs. A mean absolute relative difference (MARD) between Guardian Sensor (3) values and YSI^{TM*} plasma glucose values during YSI^{TM*} FST days defined as μ will be evaluated against the null Hypothesis:

H0: μ ≥ 20%

H1: μ < 20%

Statistical testing

At 1a), 1b), and 1c) evaluation criteria, one proportion Z test will be used for the analysis of the primary endpoint. The 97.5% lower confidence limit of the agreement rate, the mean rate in Zone A+B of Consensus Error Grid, and the mean rate in Zone A+B of Clarke Error Grid will be tested against corresponding threshold, respectively.

At 1d) evaluation criteria, one sample T test will be used and the 97.5% upper confidence limit of the MARD will be tested against corresponding threshold.

The study will be considered as a success only when the four evaluation criteria (1a), 1b), 1c), and 1d)) meet the pre-defined thresholds.

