9.4. Random Assignment and Treatment Assignment

Investigational centers will receive this random assignment generated electronically in the study database from Medtronic. Subjects will be randomly assigned to one of the following days for the in-clinic YSI™* FST: Day 1, 3-5, or 7.

Once subject is assigned to the study group, subjects will stay in that randomly assigned group during the study.

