9.6. Replacement Sensors

In the event that a sensor connecting to the transmitter which pairs to the Guardian Connect app has failed/dislodged any time prior to YSI™* FST visit or within a duration of 5 hours YSI™* FST, the subject will be asked to replace both sensors with new inserted sensors. Any re-insertion of Guardian™ Sensor (3)s will be done only once and new transmitters will be connected to the new (replacement) sensors.

In the event that a sensor connecting to the transmitter, which functions as a glucose recorder, dislodges any time prior to YSI^{TM*} FST visit or within a duration of 5 hours YSI^{TM*} FST, the subject will continue to wear the remaining sensor for the duration of the subject's sensor wear time. A replaced sensor will not be issued to the subject.

Any YSI™* FST with a duration of 5 hours or more before sensor dislodgement will be considered complete and will not need to be rescheduled.

10768467DOC Version C

Page 52 of 97

Subjects will be issued replacement Guardian[™] Sensor (3)s to be inserted at in-clinic but at the date and time specified by the in-clinic.

Subject will wear the replaced sensors for 7 days and attempt to complete the required YSI™* FST visit.

Subjects will have their YSI™* FST visit rescheduled per the original randomly assigned FST Group.

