14.8. General Considerations for Data Analysis

14.8.1. Data Collection

Primary endpoint and other descriptive endpoints will be based on real-time data collected from primary sensor. Precision analysis will be based on data collected from both sensors.

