14.10.2. Precision Analysis

Precision analysis will be performed for the two sensors worn by the same subject. Data from the primary GuardianTM Sensor (3) will be used as a reference. Data from sensor functioned as recorder will be reanalyzed using the exact calibration SMBG used for the primary sensor.

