6.6 General Considerations for Data Analysis

6.6.1 Data Collection

Analysis data source: The analysis of primary endpoints, other descriptive endpoints and simulation alert calculation will be based on both Oracle Remote Data Capture (RDC) database and external device dataset (collected sensor glucose data). The detailed specification of variables from external device data are as following:

- SG: Raw Sensor Glucose Reading
- PSGV: Predicted Sensor Glucose Reading
- SBG: Sensor Blood Glucose (values below 40 display as 40, values above 400 display as 400) elaborated below
- ROC: Rate of Change of SG
- ISIG: Interstitial Signal
- FORCALBG: Used in Calibration

The value "511" in the SG and PSGV column indicates "null". The SBG column will display saturated values of 40 if the reading was displayed as "Low" (i.e. if SG < 40 mg/dL) or 400 if the reading was "High" (i.e. if SG > 400 mg/dL) while the SG column will display 511. SG value of 40 is indicated when SG and SBG columns are equal to 40, and same for 400. SG column is used to generate the numerical calculation for sensor performance. SBG is used for alert analysis and sensor life analysis. PSGV and ROC columns are used for alert analysis.

In addition, primary endpoints, other descriptive endpoints, and functional sensor life time will be based on real-time data collected from primary sensor. Precision analysis will be based on data collected from both sensors.

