6.9 Significance Level and Statistical Analysis Software

For the statistical analysis of the primary endpoint, the level of significance will be set at one-sided 0.025. The level of significance of tests performed on other indicators will be set at two-sided 0.05 level (expect special cases). SAS® 9.4 statistical software and R3.5.2 are applied for statistical analysis.

7. Indicators and Statistical Analysis Methods

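### The investigator may choose which of two inserted sensors supplies all primary endpoint data; an unrecorded choice could tilt the result by an unknown amount, and a random designation would remove that possibility.

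*Protocol*

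**What the plan says.** Protocol 9.2.4.1 has the trained subject insert two sensors in the abdomen and connect them to transmitters. The same bullet then says "It is up to investigator's discretion on which Guardian" sensor is linked to the transmitter paired with the app. The Version B entry in Protocol section 19 lists this discretion as an added clarification, so it is deliberate.

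The choice settles where the primary data come from. Under Protocol 5.2.1 the sensor connected to a transmitter "and paired to the Guardian Connect app will be the primary sensor". Protocol 14.8.1 adds: "Primary endpoint and other descriptive endpoints will be based on real-time data collected from primary sensor". SAP 6.6.1 agrees, and gives the second sensor a role only in precision: "Precision analysis will be based on data collected from both sensors". Protocol 14.10.2 says how: "Data from sensor functioned as recorder will be reanalyzed using the exact calibration SMBG used for the primary sensor".

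If the primary sensor fails or dislodges before the frequent sample testing (FST), or within 5 hours of it, Protocol 9.6 says "the subject will be asked to replace both sensors with new inserted sensors". That creates a new pair to choose from.

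The study already has a random assignment system. Protocol 9.4 says: "Investigational centers will receive this random assignment generated electronically in the study database from Medtronic". It is used only to allocate the FST day.

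**The concern.** One discretionary act per subject decides which sensor is tested on criteria 1a to 1d. I found no rule for the choice, no requirement to make it before insertion, no field for a reason, and no planned comparison of the unselected sensor with YSI. SAP 6.6.4 says in general terms that all collected sensor data will be analysed, but no section specifies that comparison. The sensitivity analyses in SAP 7.7 cover missing data and site only.

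The protocol itself supplies a plausible mechanism. Its risk table (10.1) names badly performed insertion as a possible source of device performance problems, and lists bleeding, swelling at the site and sensor damage among the sensor risks. Staff train and supervise subjects during insertion and taping (9.2.4.3), so such signs could be seen by the team that makes the choice.

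The study has one arm and fixed thresholds, so no comparator would absorb a selection effect. A preference for the more accurate sensor would be expected to move all four criteria in the device's favour. Requiring all four to pass is therefore no protection.

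**Working it through.** **The plan's own figure (1d).** Inputs from Protocol 14.5 and SAP 6.2: assumed MARD 18, threshold 20, SD 5, 60 subjects. From SAP 6.9: "the level of significance will be set at one-sided 0.025".

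- n = (1.96 + 0.845)² × 5² / (18 − 20)² = 49.2, so 50 subjects.
- Power with 60 = Φ(2 × √60 / 5 − 1.96) = 0.873, or 0.862 with the t distribution. The stated power of at least 80% is reproduced.

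**Size of a possible tilt (illustration).** The documents give neither the between-sensor SD within a subject nor any correlation between visible cues and accuracy. Both are assumed:

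- s_w, the within-subject between-sensor SD, is taken as 25% to 75% of the plan's variance: s_w = 5 × √share, giving 2.5, 3.54 and 4.33.
- ρ, the correlation between the visible cue and sensor MARD, is taken as 0 to 0.3.
- The better-looking sensor is chosen in every subject.

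The expected maximum of two standard normal values is 1/√π = 0.564, so:

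- Expected MARD gain = ρ × s_w / √π.
- One-sided type I error of 1d, when sensors in general have a true MARD of 20, = Φ(gain × √60 / 5 − 1.96).

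Each cell shows the gain in MARD points, with the type I error in brackets:

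| Share of variance | s_w | ρ = 0 | ρ = 0.1 | ρ = 0.2 | ρ = 0.3 |
|---|---|---|---|---|---|
| 25% | 2.5 | 0 (0.025) | 0.14 (0.041) | 0.28 (0.064) | 0.42 (0.096) |
| 50% | 3.54 | 0 (0.025) | 0.20 (0.049) | 0.40 (0.090) | 0.60 (0.151) |
| 75% | 4.33 | 0 (0.025) | 0.24 (0.057) | 0.49 (0.114) | 0.73 (0.205) |

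Against the 2-point margin (20 − 18), gains of 0.14 to 0.73 are 7% to 37%. If half the choices were arbitrary, the gain would halve, to about 0.07 to 0.37 points. For 1a to 1c only the direction is argued; no size was derived.

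**With a random designation** the expected gain is 0 for any ρ, the type I error from this source stays at 0.025, and the planned 60 completers and 72 enrolled are unchanged.

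**The case against.** The strongest objection is that nothing shows the choice responds to insertion quality. Section 9.2.4.1 gives no timing, and a fixed habit, such as always pairing the left-hand sensor, fits the text equally well. No sensor-versus-YSI data exist when the choice is made. This stands: the documents support a possible tilt, not an actual one. But no provision rules out a choice after insertion, and insertion and connection come first in the bullet.

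Insertion also uses a mechanical serter (7.1.3), after the subject has shown competence on a model and under supervision (9.2.4.3). Replacement of the pair happens only once (9.6). These narrow the differences available to select on, but do not remove them.

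A reader might infer more in four respects, none of which the documents support:

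- **That the effect could never be checked afterwards.** The recorder transmitter is downloaded, its data are to be reprocessed with the primary sensor's calibration values (14.10.2), and YSI values come from the same session. The comparison is possible but not planned. It would be imperfect: primary data are real-time and calibration prompts follow the primary sensor, while recorder data are reprocessed. A recorder that dislodges is not replaced.
- **That the gain is 0.28 to 0.85 points (14% to 42% of the margin).** This results from using the full SD of 5 for s_w (0.564 × 5 × 0.1 to 0.3). That SD describes subject-level MARD and mixes between-subject with between-sensor variation, so these values are a ceiling. A range starting at ρ = 0.1 also leaves out the case of no effect.
- **That the precision analysis is biased too.** Both sensors enter it whichever is called primary. The label changes the denominator and whose calibration prompts are followed; no resulting bias has been shown.
- **That the change is free.** It needs an amendment.

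**Conclusion.** The concern holds as a possibility that the design leaves open. The investigator chooses the sensor that supplies all data for 1a to 1d, and no provision constrains, documents or checks that choice. The protocol itself accepts that poor insertion can affect performance.

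Whether any tilt would occur, and how large, cannot be determined from the documents. It is zero if visible cues do not predict accuracy or if the choice ignores them. The range of about 0.14 to 0.73 MARD points, with a 1d type I error of 0.041 to 0.205 instead of 0.025, rests on three assumptions: ρ of 0.1 to 0.3, s_w of 2.5 to 4.3, and the better-looking sensor chosen every time. It would be wrong to read this as a finding that the accuracy results are biased. The case for change is that a cheap step removes an avoidable doubt about a single-arm pivotal result, and the protocol gives no reason for the discretion.

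**What to change.** **Protocol 9.2.4.1.** Replace the discretion sentence with, for example: *After both sensors have been inserted, and before either is linked to the app, the study database randomly designates the first- or second-inserted sensor as the primary sensor. A new designation is issued for any replacement pair. The designation is recorded in the eCRF, and any departure from it is recorded as a deviation.* Withholding the designation until both sensors are in place matters: if it were known beforehand, staff or subject could take more care with the designated one. Add a cross-reference in Protocol 9.6 for replacement pairs.

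**SAP 7.7.** Add a descriptive sensitivity analysis of recorder-sensor accuracy against YSI on the 1a to 1d measures, using the reprocessed data already planned for the precision analysis. State the real-time versus reprocessed difference and the number of subjects without recorder data.

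**Cost.** One extra field in the existing assignment system, one additional analysis, and a protocol amendment that needs ethics committee approval and investigator signatures (Protocol 16.10). No change in sample size, visits, sensors or blood samples.
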